3.3 Discussion of Study Design and Choice of Control Group(s)

Study Design

This is an open-label, multicenter, PMR study in 50 pediatric patients with acquired deficiencies due to liver disease and/or pediatric patients requiring cardiac surgery or liver surgery who require replacement of multiple coagulation factors. The substitution of coagulation factors is also applicable for young children who require cardiac surgery and require priming of the cardiopulmonary by-pass circuit due to the dilution of the increased volume of the by-pass circuit relative to the circulating blood volume of the child. The study will be conducted in up to 10 sites in North America. The following number of patients is planned to be enrolled:

1. Neonates/Infants (0-2 years): a maximum of 33 patients
2. Children > 2 years and ≤ 16 years: a minimum of 17 patients

Taking into consideration the small size of the target population of children with this disease condition and intervention indication, the proposed sample size of 50 children seems appropriate to obtain sufficient safety information in a reasonable amount of time.

Control Group(s)

This is an open-label study of Octaplas to investigate its safety, tolerability and efficacy in the management of pediatric patients who require replacement of multiple coagulation factors; there is no control group.

Since the sole aim of this PMR study is the gathering of information on the safety and efficacy of Octaplas in the indicated study population, it is reasonable to omit a concurrent control group.

Target Parameter(s)

The selection of the endpoints listed in **Section 3.1** is considered adequate to provide the most relevant information on the safety and efficacy aspects of Octaplas in this setting. Therefore, these target parameters are in congruence with the study rationale.

4 STUDY POPULATION

4.1 Population Base

In total, 50 pediatric patients who require replacement of multiple coagulation factors are expected to be enrolled according to the following inclusion and exclusion criteria.

Inclusion Criteria

Patients who meet all of the following criteria are eligible for the study:

1. Patient requiring liver or cardiac surgery and/or patient with liver dysfunction associated with coagulopathy in whom replacement of multiple coagulation factors is required.
2. Voluntarily given, written and signed informed consent by the patient's legal representative(s) or guardian(s). Children deemed old enough by the Investigator/institution to understand the risks and benefits of the study should also be made aware of the risks/benefits of the study and provide written assent.
3. Male or female patient \leq 16 years of age.

Exclusion Criteria

Patients who meet any of the following criteria are not eligible for the study:

1. Patient with known homozygous congenital deficiency of protein S.
2. Patient has a history of hypersensitivity reaction to blood or plasma-derived products or to any excipient of the investigational product.
3. Patient has an already known IgA deficiency with documented antibodies against IgA.
4. Patient has a congenital factor deficiency or platelet disorder requiring plasma treatment.
5. Patient is currently participating in another study investigating a new drug product or another interventional clinical study that may impact coagulation factors or has participated during the last three (3) months.
6. Patient received FFP, FP24 or any other plasma product other than Octaplas within the last 72 hours (cryoprecipitate and albumin are not exclusionary) prior to first Octaplas infusion.
7. Patient is on ECMO (Extracorporeal Membrane Oxygenation) when plasma is ordered by the treating physician for the first infusion episode.
8. Patient is pregnant.
9. Patient is predicted to require massive blood transfusion defined as more than 40 mL per kilogram of all blood products in a 24-hour period
10. Patient is receiving plasma exchange, TPE or plasmapheresis.
11. Patient is a premature neonate defined as less than 37 weeks gestation.
12. Cardiac surgery patients who develop the need for plasma replacement greater than 72 hours after the end of the associated cardiac surgery and do not have coagulopathy due to hepatic dysfunction.

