Duration of Treatment: The study infusion(s) of Octaplas will occur over a maximum 72-hour treatment period. After the final infusion episode there will be an additional 72-hour safety follow-up period for monitoring of adverse drug reactions.	
Reference Therapy, Dose, Mode of Administration, and Batch Number(s): None.	
Study Outcome Parameters (Primary and Secondary Endpoints): Primary Endpoints: 
 • Incidence of SAEs, ADRs (e.g., allergic reactions), TEs, TEEs and hyperfibrinolytic events, beginning after the start of the first infusion episode until the final examination (end of safety follow-up period). • Clinically significant changes in laboratory parameters to assess for metabolic derangements, renal function, and hematologic implications as measured by the following: Chem 7 (metabolic panel), complete blood count (CBC) and ionized calcium. Secondary Endpoints: 
 • Clinically significant changes in hemostatic parameters as measured by the following: international normalized ratio (INR), prothrombin time (PT), activated partial thromboplastin time (aPTT), thromboelastography (TEG) or thromboelastometry (ROTEM). • Volume (dose in mL/kg) of Octaplas used per infusion episode for each patient. • Medically significant changes in vital signs. • Investigator's assessment of overall safety observed for each patient. 	
Summary of Study Procedures and Statistical Analysis Plan (SAP): Study Periods: Screening: At Screening, informed consent will be obtained from the legal representative(s) or guardian(s) of the patient. Children deemed old enough by the Investigator/institution to understand the risks and benefits of the study should provide written assent. Relevant medical history including relevant prior and on-going concomitant medications and demographic data will be recorded. The patient's eligibility will be checked based on the inclusion and exclusion criteria. A physical examination in accordance with the site's routine procedure will be performed. The patient's ABO blood group will be determined for compatibility. A pregnancy test for females at the age of \geq 11 years or of childbearing potential (if younger than 11 years old) will be performed	

Name of Sponsor/Company: Octapharma Pharmazeutika Produktionsges.m.b.H.	
Name of Investigational Product: Octaplas	Protocol Identification Code: LAS-212

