Other possible adverse reactions that may occur with the use of Octaplas are excessive bleeding caused by hyperfibrinolysis due to low levels of plasmin inhibitor in the product, thrombosis due to low levels of protein S, and citrate toxicity (hypocalcemia). The infusion rate should not exceed 1 mL/kg/min. Symptoms attributable to citrate toxicity can include fatigue, paresthesia and muscle spasms, especially in patients with liver function disorders. Because Octaplas is made from human plasma, it may carry a risk of transmitting certain infectious agents such as viruses and Variant Creutzfeldt-Jakob Disease. Other adverse reactions that have been reported in the post-marketing experience include hypersensitivity reactions including anaphylactoid and allergic type of reactions, alkalosis, cardiac arrest, circulatory overload, thromboembolism, tachycardia, respiratory arrest or failure, bronchospasm, pulmonary edema, dyspnea, tachypnea, abdominal pain, vomiting, rash, erythema, fever and/or chills, chest discomfort or pain, and seroconversions (passive transfer of antibodies).

High volumes or infusion rates may induce Transfusion Associated Volume Overload that is manifested dyspnea, hypoxia, and increasing oxygen demands. Pulmonary edema can often be seen on chest X-ray. High infusion rates may rarely cause cardiovascular effects as a result of citrate toxicity (fall in ionized calcium), especially in patients with liver function disorders. Octaplas should be used with caution in patients with risks for thrombotic complications because of the potential for increased risk of venous thromboembolism. In order to reduce the risk for venous thromboembolism, appropriate measures should be considered in all patients at risk for thrombotic complications subjected to coagulation factor support for an extended period of time (e.g., during long-term, large-volume therapeutic plasma exchange [TPE]) using Octaplas.

Administration of Octaplas must be based on ABO-blood group compatibility with the recipient. Hemolytic reactions can occur with ABO blood group mismatches. In emergency cases, blood group AB can be regarded as the universal plasma since it can be given to all patients.

Octaplas should not be used in patients with:

- Immunoglobulin A (IgA) deficiency
- Severe deficiency of protein S
- History of hypersensitivity to FFP or to plasma-derived products
- History of hypersensitivity reaction to Octaplas

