5.5 Preparation and Method of Administration

Octaplas will be used per the approved labeling for the product (see **Appendix 1**). Octaplas will be administered based on ABO-blood group compatibility. In urgent cases and in the circumstances that no same blood group is available (type A donor plasma for type A

recipient), patient can be administered plasma that is compatible to recipient's blood group (e.g., donor AB plasma can be administered to recipient with blood group A).

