6 STUDY CONDUCT

6.1 Study Periods

Screening

The following assessments will be performed at Screening:

- Obtaining voluntarily given, written (signed and dated) informed consent by the patient's legal representative(s) or guardian(s). Children deemed old enough by the Investigator/institution to understand the risks and benefits of the study should also be made aware of the risks/benefits of the study and provide written assent. Patients determined to have a reasonable probability to receive intra-operative plasma transfusion according to the Investigator's clinical judgment may also be approached for consent to participate. If these patients are subsequently not prescribed plasma intra-operatively or postoperatively they will be determined to be a screening failure and not included in the analysis.
- Review of inclusion and exclusion criteria.
- Physical examination (see **Section 7.3.6**).
- Relevant medical history including prior medications (taken within 7 days prior to time 0 (study drug given) and on-going concomitant medication(s)).
- Demographic data (height, BW, gender, date of birth, ethnicity).
- Determination of ABO blood group for compatibility.

- Pregnancy testing for females at the age of ≥ 11 or of childbearing potential (if younger than 11 years old). Results must be negative for the female patient to be in the study.
- Documentation of type of surgical procedure indicated for the patient and important operative interventions.
- Ordering of plasma if clinically indicated per physician discretion.

Pre-Infusion (Immediately Before First Infusion Episode)

The following assessments will be performed before the first infusion episode:

- Vital signs (see **Section 7.3.6**).
- Blood sample(s) for hemostatic parameters (see **Section 7.2.1**).
- Blood sample(s) for laboratory parameters (see **Section 7.3.5.3**).

Study Treatment Period

The number of infusion episodes and actual total volume (dose in mL/kg) of Octaplas administered to a patient within the 72-hour treatment period will depend on the clinical setting and physician discretion. After 72 hours from the start of the first infusion of Octaplas, the study treatment period will end. The following procedures will be performed during the study treatment period:

- Administration/infusion of Octaplas.
- Vital signs.
- Monitoring of ADRs (refer to **Section 7.3.2.1** for definition), TEs, TEEs, hyperfibrinolytic events and concomitant medications.

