10.4 Protocol Amendments

Any prospective change to the protocol will be agreed between the Investigator (coordinating investigator in multi-center studies) and the Sponsor prior to its implementation. Any such amendments will be submitted to the IEC(s)/IRB(s) and/or competent authority responsible as required by applicable regulations. IEC/IRB approval will at a minimum be requested for any change to this protocol which could affect the safety of the patients, the objective/design of the study, any increase in dosage or duration of exposure to the IMP, an increase in the number of patients treated, the addition of a new test or procedure, or the dropping of a test intended to monitor safety.

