4 CONTRAINDICATIONS

Do not use Octaplas in patients with:

- IgA deficiency
- Severe deficiency of Protein S
- History of hypersensitivity to fresh frozen plasma (FFP) or to plasma-derived products including any plasma protein
- History of hypersensitivity reaction to Octaplas

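### Exclusion 3 bars known IgA deficiency only when anti-IgA antibodies are documented, although section 1.3 and the label bar Octaplas in IgA deficiency without that condition

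*Protocol*

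**What the plan says.** The third exclusion criterion, in the protocol synopsis and again in section 4.1, is: "Patient has an already known IgA deficiency with documented antibodies against IgA".

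Section 1.3 (Benefit-Risk Statement) has a do-not-use list. It opens "Octaplas should not be used in patients with", and its first item is "Immunoglobulin A (IgA) deficiency". The package insert in Appendix 1, section 4, opens "Do not use Octaplas in patients with" and also puts IgA deficiency first. Neither list mentions antibodies.

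Section 5.5 ties the study to the label: "Octaplas will be used per the approved labeling for the product".

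On how eligibility is decided, the synopsis says that the patient's "eligibility will be checked based on the inclusion and exclusion criteria", and the screening list in section 6.1 contains the step "Review of inclusion and exclusion criteria". That screening list includes no IgA or anti-IgA test.

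**The concern.** The eligibility list should be at least as strict as the contraindications that the protocol itself states. Here it is looser. A site that works through section 4.1 as written can enroll a child whom section 1.3 and the label say not to treat.

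The study also does not generate the antibody result on which the criterion depends. A child with a recorded IgA deficiency who has never been tested for anti-IgA passes by default.

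What is at stake is participant safety and the internal consistency of the protocol, not a statistical result. Safety is the primary objective, and the label says that the product has not been evaluated in pediatric patients. One monitoring point follows. SAP section 7 gives entry-criterion violations as an example of deviations to review, but a child of this kind violates no entry criterion as written, so a check built on the entry criteria would not flag the case.

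**Working it through.** There is no figure in the plan to reproduce. The check is a comparison of texts, followed by a sense of scale.

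**Who is excluded and who is contraindicated**

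| Source | Condition |
|---|---|
| Exclusion 3 (synopsis and 4.1) | IgA deficiency already known **and** anti-IgA antibodies documented |
| Section 1.3 | IgA deficiency |
| Package insert, section 4 | IgA deficiency |

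The excluded group is a strict subset of the contraindicated group. Among children whose deficiency is already on record, the gap consists of those whose antibodies are negative, untested or undocumented.

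**Does anything else in section 4.1 close the gap?**

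- Exclusion 2 requires an earlier hypersensitivity reaction to blood or plasma products or to an excipient. It catches a child in the gap only if such a reaction has already happened.
- No other criterion mentions IgA.
- Section 6.1 adds no relevant test.
- Section 5.5 may stop the infusion, but it does not alter the eligibility list. It confirms that the label's contraindication applies in this study.

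**Scale (assumed inputs)**

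Let p be the share of otherwise eligible children with a known IgA deficiency and no documented antibodies. The documents do not give p. The number of patients, 50, comes from section 9.1. Treating patients as independent:

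- expected number = 50 × p
- chance of at least one = 1 − (1 − p)^50

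| Assumed p | Expected number in 50 | Chance of at least one |
|---|---|---|
| 0.01% | 50 × 0.0001 = 0.005 | 1 − 0.9999^50 = 0.5% |
| 0.1% | 50 × 0.001 = 0.05 | 1 − 0.999^50 = 4.9% |
| 1% | 50 × 0.01 = 0.5 | 1 − 0.99^50 = 39.5% |

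These count children who would pass the eligibility check, not reactions. The documents give no reaction rate for this group. The range spans a factor of 100 and nothing in the documents favors one value over another.

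**The case against.** The strongest reply is that dosing is already barred. Section 1.3 is in the body of the protocol, section 5.5 binds use to the label, plasma is ordered at the physician's discretion, and under section 4.3 the investigator can withdraw a child in the child's interest. A child consented before surgery who never receives Octaplas becomes a screening failure and stays out of the safety population. Read as a whole, the protocol would more often produce a query or a wasted consent than a contraindicated infusion. This stands as a reduction of the practical risk. It does not remove the conflict, because the site's eligibility check is made against the list in section 4.1.

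Second, no benefit to the individual child is shown. The label describes the product's protein content as comparable to that of healthy donors apart from protein S and alpha2-antiplasmin, so an excluded child who still needs plasma may receive another product that contains IgA, without the study's scheduled monitoring. This also stands: what can be claimed for the fix is agreement between eligibility and contraindication, not a demonstrated fall in risk.

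Third, the wording may be deliberate. It is the same in both places, and exclusion 1 is likewise narrower than the label's protein S contraindication, which suggests an attempt to turn label terms into facts that can be read from the chart. But a deficiency that is already known can be read from the chart without the antibody condition, and no section gives a reason for adding it. Intent cannot be settled from the documents.

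Fourth, the supplied protocol is dated 19-Nov-2016, whereas the SAP (section 1) was written against Version 10 of 29-Nov-2017. Enrolment text differs between the two sources: SAP section 4.2 gives age quotas of 37 and 13, protocol section 3.3 gives 33 and 17. Completion was planned for the fourth quarter of 2017 (protocol section 3.2). Whether an amendment is still needed cannot be known from these documents.

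**Conclusion.** The concern holds. As written, exclusion 3 is narrower than the protocol's own do-not-use list and the appended contraindication, and no other criterion closes the gap. The text comparison is certain and rests on no outside source.

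The consequence is small in expectation. It is confined to children with an IgA deficiency already on record and no documented antibodies, probably very few among 50, and any number put on it depends on the assumed p. Sections 1.3 and 5.5 make an actual infusion less likely. No analysis is affected. It should still be corrected, because it is a safety inconsistency in a study whose primary purpose is safety and the correction is very cheap, provided that the version in force still carries the wording and patients are still being enrolled.

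**What to change.** 1. Check Version 10 and the enrolment status. If Version 10 already carries the change, or enrolment has closed, no amendment is needed.
2. Otherwise, delete the antibody condition from exclusion 3 in the synopsis and in section 4.1, so that an already known IgA deficiency is enough to exclude. Apply the change prospectively and add no IgA or anti-IgA testing. A child whose deficiency is not known would still pass, which cannot be avoided without a test.
3. If the sponsor wants to keep the antibody condition, give the reason in section 1.3 and write an exception into section 5.5, since both now say otherwise.

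**Cost.** One phrase in two places, and ethics approval of the amendment, since section 10.4 says: "IEC/IRB approval will at a minimum be requested for any change to this protocol which could affect the safety of the patients". There is no extra blood draw and no change to the SAP. The downside is that a few children with known IgA deficiency and no documented antibodies lose access to the study and may receive another plasma product instead.

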4.2 Prior and Concomitant Therapy

Details of relevant current and concomitant medications administered during the trial period will be recorded on the CRF. Relevant medications are defined as follows:

- Plasma products (e.g., octaplas™, regular plasma products, etc.) and all other blood products that are administered.
- Antifibrinolytics (ε-aminocaproic acid or tranexamic acid) and any other pharmaceutical pro- or anti-coagulants such as recombinant activated factor VII, any of the prothrombin complex concentrates, or fibrinogen concentrates.
- Vaso-active agents (epinephrine, norepinephrine, vasopressin, Milrinone, phenylephrine, Antidiuretics (desmopressin, DDAVP, DesmoMelt, Stimate, Minirin, etc.).
- Colloids (e.g., albumin, hydroxyethyl starches).
- Medications (including steroids) taken to treat or prevent ADRs (to Octaplas)
- Other medications that the Investigator considers relevant to report for this trial.

Routine medications that are considered standard and/or that have little or no impact on the study data results are not to be entered into the CRF (e.g., anesthesia medications, beta blockers, etc.). Any concomitant medications or changes thereof must be recorded. If the change influences the patients' eligibility to continue in the trial, the Sponsor must be informed.

Permitted Concomitant Therapy

The following concomitant medications are permitted:

- calcium-gluconate given IV in case of hypocalcemia (due to citrate toxicity),
- antihistamines and glucocorticoids given IV in case of anaphylactoid reactions, and
- red blood cells, platelet units if medically indicated.

It is permitted for patients to receive Octaplas or other plasma products (please see exceptions below) during the 72-hour follow-up period if medically indicated.

Although patient's requiring ECMO at study entry are excluded, ECMO is permitted therapy while on study if it is determined to be medically indicated after the start of the first infusion.

Forbidden Concomitant Therapy

Single donor plasma (e.g., FFP, FP24, thawed plasma, etc.) should be avoided during the Treatment and Follow-up study periods. Patients receiving single donor plasma during the Treatment or Follow-up periods should be withdrawn from the trial.

Plasma exchange, TPE or plasmapheresis is not permitted during the study. Patients who develop the need for and undergo plasma exchange or plasmapheresis during the Treatment or Follow-up periods will be withdrawn from the trial.

4.3 Withdrawal and Replacement of Patients

Premature Patient Withdrawal

Patients have the right to withdraw from the study at any time for any reason, without the need to justify their decision. The Investigator also has the right to withdraw patients in case of ADRs, protocol violations, or other reasons. Since an excessive rate of withdrawal can render the study non-interpretable, the unnecessary withdrawal of patients must be avoided.

For any discontinuation after study entry, the Investigator will obtain all the required details and document the reason(s) for discontinuation in the CRF. If the reason for withdrawal of a patient is an ADR, the main specific event or laboratory test will be recorded in the CRF, and the Investigator will make thorough efforts to clearly document the outcome.

Moreover a patient may be withdrawn from the study prior to completion for any of the following reasons:

- Whenever the patient/legal representative(s)/guardian(s) decides it is in the patient's best interest to withdraw
- Whenever the Investigator decides it is in the patient's best interest to be withdrawn
- Pregnancy

For any premature patient withdrawal after study entry, the Investigator will obtain all the required details and document the reason(s) for discontinuation in the CRF. Data of patients withdrawn prematurely will be included in the safety analysis.

Patients consented (enrolled) into the study pre-operatively for cardiac and liver surgery will be considered screening failures if they do not receive Octaplas intra-operatively or post-operatively. Patients who are consented but do not receive Octaplas intra-operatively will be eligible for study treatment while they remain in the intensive care unit. Patients who are discharged from the intensive care unit without being treated with Octaplas will be considered a screening failure.

Patient Replacement Policy

There is no patient replacement policy defined for this protocol. Fifty (50) pediatric patients will be treated in the study.

